7.3.4.1. Safety Stopping Rules

7.3.4.1.1. Liver Enzymes

In any increase of ALT or AST to ≥ 2 times ULN the “Guidance on Safety Monitoring” (see [Appendix 10](#)) should be thoroughly followed.

In the following circumstances, study drug will be discontinued immediately and liver enzymes will be monitored according the guidance in [Appendix 10](#):

- Any increase in ALT or AST to ≥ 3 times ULN, combined with INR >1.5 or total bilirubin $>2\times$ ULN
- Any increase in ALT or AST to ≥ 3 times ULN, which is accompanied by nausea, vomiting, fever, rash, or eosinophilia
- Any increase in ALT or AST to levels ≥ 5 but <8 times ULN, which is persistent for ≥ 2 weeks of repeated measurements.
- Any increase in ALT or AST to levels ≥ 8 times ULN
- In any case where monitoring of liver enzymes cannot be performed according to the protocol guidance (see [Appendix 10](#))

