8.2.5. Safety Laboratory Evaluations

Unless specified otherwise all laboratory testing will be performed by a central laboratory facility. In cases in which close-follow-up is required, as described in [Appendix 10](#), certain tests may be performed in a local laboratory.

Laboratory tests (including pregnancy test for women of child bearing potential) will be performed at each scheduled study visit (in unscheduled visit upon need).

The following tests will be performed:

* Those tests may also be performed in a local lab according to the Safety Monitoring Guideline.

- Serum Chemistry
 - Glucose
 - Creatinine (including GFR estimation)
 - Bilirubin (direct and total)*
 - Urea
 - AST (SGOT)*
 - ALT (SGPT)*
 - GGT*
 - Lipid profile (total cholesterol, high density lipoprotein [HDL], low density lipoprotein [LDL], triglycerides) under fasting conditions.
 - Pancreatic Amylase
 - Lipase will be tested in case of abnormal pancreatic amylase result (see [Appendix 10](#) for guidance on monitoring subjects with elevated pancreatic amylase levels)
 - Total Protein*
 - Albumin*
 - Alkaline Phosphatase*
 - hs-CRP
 - CPK

- In case of abnormal CPK result: troponin and CPK-MB will be tested
- In case of CPK >2000 U/L: urine myoglobin will be tested and the following tests will be repeated: CPK, CPK MB, blood urea nitrogen, creatinine, electrolytes including potassium, calcium, phosphate, hs-CRP and fibrinogen
- Pregnancy tests:
 - Serum β-hCG pregnancy tests (to be performed in women of child-bearing potential, at all scheduled study visits)
 - Urine β-hCG pregnancy test (to be performed in women of child-bearing potential), at all scheduled study visits (excluding Termination) and every 28 ± 2 days, at home.

Pregnancy tests do not need to be performed for women who have discontinued study treatment but are continuing to attend scheduled study visits for follow-up.

- Electrolytes
 - Sodium
 - Potassium
 - Phosphorous
 - Calcium
- Coagulation
 - Fibrinogen
 - INR (to be performed in local laboratory, only if required according to Safety Monitoring Guidance, in [Appendix 10](#))
- Hematology
 - Hemoglobin
 - MCH
 - MCV
 - MCHC
 - Hematocrit
 - Red Blood Cells (RBC)

- White Blood Cells + differential count*
- Platelets count
- Serology (to be performed only in a confirmed abnormality of liver enzymes, according to [Appendix 10](#)):
 - Anti-HAV IgM antibodies
 - Hepatitis B Surface antigen
 - Anti-HBc IgM antibodies
 - Anti- HCV IgG antibodies

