^p Thorough medical history with a focus on liver disease: Personal or family history of liver disease; personal history of a systemic disease with potential liver involvement; exposure to alcohol, medications (prescription or OTC), herbal preparations, dietary supplements, recreational drugs, special diets or environmental chemical agents; potential exposure to infectious agents (eg, travel to developing countries, history of potential exposure to blood or blood products, high-risk sexual relations) and any additional information deemed relevant by the investigator. Physical examination – including signs of chronic liver disease

2. In case Baseline value was above ULN and ALT or AST is ≥ 2 times the Baseline value.

Upon confirmation of the abnormality as noted above, the following additional evaluations should be performed and results should be recorded in the eCRF.

Additional Tests/Evaluations

- Serology for Hepatitis A, B, and C viruses (central laboratory).
- Serology for autoimmune hepatitis: anti-nuclear antibodies, ASMA (Anti Smooth Muscle Antibodies), anti-LKM (Liver Kidney Microsomal) antibodies (central laboratory).
- An ultrasound examination of the liver and biliary tract.
- Other diagnostic tests/consultations, as deemed necessary by the investigator e.g. serology for hepatitis E virus in case of travel to endemic geography)

Observation and Follow-Up (to be performed after the abnormality was confirmed as above)

1.1.1. ALT or AST $\geq 3 \times$ and $\leq 5 \times$ ULN (if Baseline value is $\geq 2.5 \times$ ULN, ALT or AST $\geq 3.5 \times$ ULN and $\leq 5 \times$ ULN)

In addition to the above procedures required for any elevation to levels $>3 \times$ ULN:

- ALT, AST, GGT, ALP, total and direct bilirubin, CBC and differential (to assess for eosinophilia) and INR should be monitored on days 5 (± 2), 8 (± 2), 14 (± 2), and 28 (± 2). On at least 1 of these days, the test should be performed centrally. (INR should be sent to a local laboratory only.)
- In cases where a local laboratory is used, the results should be recorded in the eCRF, accompanied by the reference range of the relevant measurements.

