- Should the abnormality ($\geq 3 \times$ ULN in case Baseline within normal range or $\geq 2 \times$ ULN in case the Baseline value was above ULN, but still $< 5 \times$ ULN) persist further, the subject will be followed according to the investigator's discretion, but at least once a month a blood sample for ALT, AST, GGT, ALP, and total and direct bilirubin should be sent to the central laboratory.

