1.1.3. ALT or AST \geq 8xULN

In addition to the above procedures required for any elevation to levels >3 xULN:

- The study drug should be discontinued immediately and the early termination visit should be performed.
- For follow-up guidance, please see below section "*Follow-up of Liver Enzymes after Stopping-Rules are met*".

1.2. Stopping Rules:

In the following circumstances, the study drug will be discontinued immediately:

- Any increase in ALT or AST to $\geq 3 \times \text{ULN}$, combined with INR > 1.5 or total bilirubin $> 2 \times \text{ULN}$
- Any increase in ALT or AST to $\geq 3 \times \text{ULN}$, which is accompanied by nausea, vomiting, fever, rash, or eosinophilia
- Any increase in ALT or AST to levels $\geq 5 \times$ but $< 8 \times \text{ULN}$, which is persistent for ≥ 2 weeks of repeated measurements
- Any increase in ALT or AST to levels $\geq 8 \times \text{ULN}$
- In any case where monitoring of liver enzymes cannot be performed according to the protocol guidance

1.2.1. Follow-Up of Liver Enzymes After Stopping-Rules Are Met:

- A subject who meets the above criteria for discontinuation of the study drug should be invited to the site to return the study drug. Early termination visit activities should be performed as soon as possible.
- Liver enzymes should be monitored until normalization or stabilization of the abnormality, according to the discretion of the investigator.
- In any case, following early termination, the minimal follow-up period will be 4 weeks and will include measurement of liver enzymes at least QW (may be performed in a local laboratory, with at least 1 test being sent to the central laboratory).
- Every effort should be made to complete the additional tests/ evaluations, as described above.

2. Use of Moderate/Strong CYP3A4 Inhibitors

Laquinimod PK is affected by moderate and strong CYP3A4 inhibitors; therefore, moderate/strong CYP3A4 inhibitors are disallowed during study and 30 days after the last dose has been administered. A partial list of commonly used CYP3A4 inhibitors is presented in [Appendix 5](#).

3. Cancers diagnosed during the study

Subjects that are diagnosed with a malignant solid or liquid tumor while participating in the study should stop study drug.

4. Guidance on Monitoring Subjects with Elevated Pancreatic Amylase Levels

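### When an ALT/AST elevation at ≥3 but <5×ULN persists past Day 28 on drug, Appendix 10 requires no further INR and a differential only at scheduled visits, yet both remain immediate-stop criteria

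*Combined protocol and SAP*

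**What the plan says.** The stopping rules are in section 7.3.4.1.1 and are repeated in Appendix 10, section 1.2. They open with "In the following circumstances, study drug will be discontinued immediately". Two of them concern ALT or AST at ≥3×ULN. One applies when the elevation is "combined with INR >1.5 or total bilirubin" >2×ULN, the other to an elevation "which is accompanied by nausea, vomiting, fever, rash, or eosinophilia". Each listed item is sufficient alone, and neither rule expires.

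Monitoring for the ≥3 to ≤5×ULN band is in Appendix 10, section 1.1.1. In the first month, liver enzymes, bilirubin, "CBC and differential (to assess for eosinophilia) and INR should be monitored on days 5", 8, 14 and 28 (each ±2). If the abnormality persists but stays below 5×ULN, follow-up passes to the investigator's discretion. The floor is that "at least once a month a blood sample for ALT, AST, GGT, ALP, and total and direct bilirubin should be sent" to the central laboratory. That bullet also covers subjects whose baseline was above ULN and who persist at only ≥2×ULN.

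Section 8.2.5 lists the tests done at every scheduled visit. They include "White Blood Cells + differential count". INR is listed too, but is "to be performed in local laboratory, only if required according to Safety Monitoring Guidance", meaning Appendix 10.

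**The concern.** After Day 28 the two stop criteria stay in force, but the tests that would reveal them leave the required monthly panel. A site that follows the floor exactly can keep a subject on drug at ≥3 but <5×ULN without ever repeating INR, and with eosinophils counted only when a scheduled visit falls due. An isolated INR rise would then have no required test to show it. A symptom-free eosinophilia could wait until the next visit.

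The duration is open-ended. The two-week persistence stop applies only at ≥5×ULN, so a subject may remain in the lower band, on drug, for as long as the study runs. The protocol treats both tests as relevant in this band up to Day 28, and section 1.1.2 requires them twice weekly in the next band up. It gives no reason for dropping them in between.

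**Working it through.** The plan gives no figure to reproduce. The check compares stop criteria with required tests and then counts from the visit schedule.

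**Criteria against required tests, ALT/AST ≥3 but <5×ULN**

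| Stop criterion | Required up to Day 28 (1.1.1) | Required after Day 28 |
|---|---|---|
| Total bilirubin >2×ULN | Days 5, 8, 14, 28 | Monthly |
| INR >1.5 | Days 5, 8, 14, 28 | None |
| Eosinophilia | Days 5, 8, 14, 28 | Scheduled visits only |

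Two provisions might seem to restore INR, but do not. Section 8.2.5 refers back to Appendix 10. The mandatory list in Appendix 10, section 1.1, which includes INR, applies to samples sent to a local laboratory, and the monthly minimum goes to the central one. INR is therefore measured four times by requirement up to Day 28 and not at all afterwards.

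**Monthly samples without a required eosinophil count**

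From section 7.1: a month is 30 days; visits have a ±7-day window; they are 3-monthly from open-label Month 3 to Month 24 and 6-monthly after. Assumed, because the documents do not say: the elevation is found at a scheduled visit, the result arrives 1 to 7 days later (Day 0 is the day it is received), and monthly samples follow Day 28 every 30 days, on Days 58, 88, 118, 148, 178 and 208.

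- 6-monthly visits: interval 180 ± 14 = 166 to 194 days. Subtracting 1 to 7 days puts the next visit on Day 159 to 193. Samples strictly before it: 4 if the visit is on Day 159 to 178, 5 if on Day 179 to 193.
- 3-monthly visits: interval 90 ± 14 = 76 to 104 days. The next visit is on Day 69 to 103. Samples before it: 1 if on Day 69 to 88, 2 if on Day 89 to 103.
- Moving Day 28 within its ±2 window leaves the counts at 4 to 5 and 1 to 2.
- While visits are monthly (up to Month 3) there is no added gap.

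**How many subjects**

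Section 3.4.1.1, Table 4, laquinimod 0.6 mg with normal baseline, peak >3 to ≤5×ULN: ALT 30/888 = 3.4% (placebo 5/930 = 0.5%); AST 9/950 = 0.9%. Section 21.1 gives 110 ongoing subjects at Amendment 10. For illustration, 30/888 × 110 = 3.7 subjects for ALT and 9/950 × 110 = 1.0 for AST. These are subjects ever peaking in the band; persistence past Day 28 is a subset that the documents do not quantify.

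**The case against.** The strongest reply is that this is a deliberate step-down. Before the monthly floor applies, the subject has had a confirmatory test, viral and autoimmune serology, a liver ultrasound and four rounds of INR and differential. Nothing obliges the later minimum to match the first month, and the investigator may add either test.

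Other safeguards also remain:

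- Bilirubin, the alternative trigger in the same rule, stays monthly.
- Albumin and total protein are measured at scheduled visits.
- Symptoms compatible with drug-induced liver injury call for an unscheduled visit, where vital signs and AE evaluation are mandatory (7.3.6).
- Chronic liver disease with impaired function is a separate stop (7.3.4.1.4).
- Reaching 5×ULN brings back INR and differential twice weekly.

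All of this stands and keeps the gap narrow, but it does not close it. Discretion permits a test without requiring it, and laboratory tests at an unscheduled visit are optional. Neither symptoms nor bilirubin will show an isolated INR rise or a silent eosinophilia.

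A reader might infer that eosinophilia is no longer looked for at all after Day 28. The documents do not support that: section 8.2.5 requires a differential at every scheduled visit. For eosinophils the gap is one of frequency; only for INR is it one of absence.

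It could also be said that a monthly local INR would bring the whole mandatory local panel with it and duplicate the central draw. Sections 1.1.1 and 1.1.2 already combine central liver panels with an INR sent locally, so that reading is not forced.

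The objection on scale is fair. Table 4 describes patients followed for up to 2 years in the pivotal studies. Elevations generally arose within 6 months of starting, so long-term extension subjects probably have fewer. The Amendment 10 procedures appear in the schedules from Month 24 onward, which suggests that ongoing subjects are past Month 24 and that the 3-monthly counts may no longer matter.

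**Conclusion.** The point holds as a cheap safety improvement. For a subject kept on drug with ALT or AST persisting at ≥3 but <5×ULN after Day 28, no INR is required, and a differential is required only every 3 or 6 months with scheduled visits rather than with the monthly liver sample. Both findings remain stand-alone immediate-stop criteria.

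The INR conclusion follows from the text alone. The eosinophil counts (4 to 5 samples on 6-monthly visits, 1 to 2 on 3-monthly) depend on the assumed result lag and draw dates. Few subjects are likely affected: about 4 of 110 is an illustration of those ever peaking in the band and probably overstates current numbers. It should not be read as evidence that a stop has been missed; the documents show none.

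**What to change.** Add to the persistence bullet in Appendix 10, section 1.1.1: *and, for as long as ALT or AST remains ≥3×ULN on study drug, CBC with differential in the same monthly central sample and an INR at a local laboratory.* The ≥3×ULN condition matters. Without it the change would also reach subjects with baseline above ULN who persist at 2 to <3×ULN, to whom these two stop rules do not apply; their panel should stay as it is.

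The longest required interval for each test would then be about 30 days. As written, there is no limit for INR, and the interval for the differential is up to 194 days on 6-monthly visits.

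The cost is one line of text and, per affected subject per month, one CBC tube at a draw that already takes place and one tube for the local INR. The INR result and its reference range must also be entered in the eCRF.

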1.1.2. ALT or AST $\geq 5 \times$ but less than $8 \times$ ULN

In addition to the above procedures required for any elevation to levels $>3 \times$ ULN:

- ALT, AST, GGT, ALP, total and direct bilirubin, CBC and differential count (to assess for eosinophilia), and INR should be monitored twice a week.

- At least for every other measurement, the tests should be sent to the central laboratory. The rest of the tests may be sent to a local laboratory. INR should always be sent to a local laboratory.

1.1.3. ALT or AST \geq 8xULN

In addition to the above procedures required for any elevation to levels >3 xULN:

- The study drug should be discontinued immediately and the early termination visit should be performed.
- For follow-up guidance, please see below section "*Follow-up of Liver Enzymes after Stopping-Rules are met*".

1.2. Stopping Rules:

In the following circumstances, the study drug will be discontinued immediately:

- Any increase in ALT or AST to $\geq 3 \times \text{ULN}$, combined with INR > 1.5 or total bilirubin $> 2 \times \text{ULN}$
- Any increase in ALT or AST to $\geq 3 \times \text{ULN}$, which is accompanied by nausea, vomiting, fever, rash, or eosinophilia
- Any increase in ALT or AST to levels $\geq 5 \times$ but $< 8 \times \text{ULN}$, which is persistent for ≥ 2 weeks of repeated measurements
- Any increase in ALT or AST to levels $\geq 8 \times \text{ULN}$
- In any case where monitoring of liver enzymes cannot be performed according to the protocol guidance

1.2.1. Follow-Up of Liver Enzymes After Stopping-Rules Are Met:

- A subject who meets the above criteria for discontinuation of the study drug should be invited to the site to return the study drug. Early termination visit activities should be performed as soon as possible.
- Liver enzymes should be monitored until normalization or stabilization of the abnormality, according to the discretion of the investigator.
- In any case, following early termination, the minimal follow-up period will be 4 weeks and will include measurement of liver enzymes at least QW (may be performed in a local laboratory, with at least 1 test being sent to the central laboratory).
- Every effort should be made to complete the additional tests/ evaluations, as described above.

2. Use of Moderate/Strong CYP3A4 Inhibitors

Laquinimod PK is affected by moderate and strong CYP3A4 inhibitors; therefore, moderate/strong CYP3A4 inhibitors are disallowed during study and 30 days after the last dose has been administered. A partial list of commonly used CYP3A4 inhibitors is presented in [Appendix 5](#).

3. Cancers diagnosed during the study

Subjects that are diagnosed with a malignant solid or liquid tumor while participating in the study should stop study drug.

4. Guidance on Monitoring Subjects with Elevated Pancreatic Amylase Levels

Pancreatic amylase will be measured at each study visit. Lipase will be tested in case of abnormal pancreatic amylase results and on all follow-up visits until normalization of pancreatic amylase level. In case of suspected pancreatitis, the subject should undergo a thorough clinical evaluation including an abdominal CT scan as soon as possible in order to clarify the diagnosis and enable assessment of severity of this condition. An MRI may be performed as an alternative to the CT scan.

5. Liver Impairment

Subjects who develop any chronic liver disease associated with liver functional impairment while participating in the study should stop study medication.

6. Renal Impairment

Subjects who develop renal disease associated with moderate or severe functional impairment, defined as glomerular filtration rate (GFR) ≤ 60 mL/min/1.73 m², while participating in the study should stop study medication temporarily and the GFR assessment should be repeated. If the renal impairment is confirmed (GFR ≤ 60 mL/min/1.73 m²), the subject should stop study medication permanently.

7. Management of pregnancy and pregnancy testing during the study

Exposure to laquinimod during pregnancy should be avoided.

To further emphasize the importance of use of effective contraception and avoidance of pregnancy under laquinimod exposure (see Section 3.4), and to reduce as much as possible the exposure to laquinimod if a pregnancy occurs despite all recommended measures, all subjects who are women of childbearing potential will be instructed about the teratogenicity and potential delayed risks for a child exposed in uterus to laquinimod. These subjects will also be counseled about the importance of using two acceptable methods of birth control throughout the entire treatment duration and until 30 days after the last dose of treatment was administered and about the need to stop treatment immediately if pregnancy is suspected.

Women of child-bearing potential (for example women who are not postmenopausal or surgically sterilized) must practice an acceptable method of birth control for 30 days before taking the study drug and two acceptable methods of birth control for the duration of the study and until 30 days after the last dose of study medication. Acceptable methods of birth control include: intrauterine devices, barrier method (condom or diaphragm with spermicide) and hormonal methods of birth control (e.g. oral contraceptive, contraceptive patch, long-acting injectable contraceptive).

The subjects' understanding of the importance of preventive pregnancy measures and their ability to follow the required instructions will be ascertained by the investigator and recorded in source documents at every visit. Any female subject who becomes pregnant during the study will discontinue her participation in the study and will not perform the activities described for scheduled follow-up visits.

At each scheduled visit, the subject will undergo a urine β -hCG test. In addition, a serum pregnancy β -hCG test will be performed at each visit to the site. Subjects who have discontinued study drug but are continuing to attend study visits for follow-up do not need to perform pregnancy tests.

1. In case the urine test is negative, study drugs will be dispensed according to planned visit tasks (see Section 7.2).
 - a. If the blood test is positive, the subject will be contacted immediately and instructed to stop taking the study drug. The subject should be invited to attend an early termination visit.
 - b. If the blood test is negative – study procedures will be undertaken as planned.
2. In case the urine test is positive – the study drug will not be dispensed (if this occurs at Baseline visit, the subject will not be eligible to participate in the study and will be considered as a screening failure)
 - a. If the blood test is positive, the subject will be invited to the site for an early termination visit
 - b. If the blood test is negative, the subject will be contacted and informed about the test result and the study drugs will be sent to her by courier as soon as possible.
3. Starting from visit 3 (Month 3), the following actions will be taken:
 - a. The subject will be provided with home pregnancy urine β -hCG test kits and will be guided how to perform the test.
 - b. The subject will be instructed to perform the test in monthly intervals (every 28 (± 2) days) from the visit date. These dates should be recorded by the study coordinator and a telephone call, will be scheduled to be performed within 72 hours of the urine test date.
 - c. A mandatory phone call will be performed by the Study Neurologist/ Physician or by the site's nurse/ study coordinator every month in order to verify whether the test has been performed and to record the result of the test in the subject's file. In case of a suspected pregnancy, the subject will be instructed to stop taking the study drug and arrive to the site as soon as possible for an unscheduled visit, with the remaining study medications. In the site, a quantitative urine β -hCG pregnancy test should be performed and the rest of the activities will be as in 2.

In case of an established diagnosis of pregnancy, the Study Physician/Neurologist should discuss with the subject the potential teratogenicity and delayed risks for a child exposed in utero to laquinimod. The possibility of termination of the pregnancy should be discussed. In case the subject decides to continue the pregnancy, she will be followed to determine outcome, including spontaneous or elective termination, details of birth, and presence or absence of any birth defect, congenital abnormalities or maternal and newborn complications.

Female subjects of child-bearing potential who might want to get pregnant in the future, and might be interested in continuing taking laquinimod after giving birth and have stopped breastfeeding may be able to re-enroll in the study after meeting inclusion/exclusion criteria below. Re-enrollment will be permitted on a case-by-case basis. Notwithstanding, Teva is under no obligation to re-enroll such subjects and reserves the right to re-enroll or reject enrolment of such returning subjects for no reason and on its sole discretion. A new informed consent form should be signed before re-enrollment.

Inclusion Criteria for returning subjects

Subjects must meet all inclusion criteria in order to be eligible for the study:

1. Subjects must have completed the Termination visit of LAQ/5063 OL phase (completion of all Termination visit activities) according to the LAQ/5063 OL protocol.
2. Subjects must be ambulatory with Kurtzke's EDSS score of 0-5.5 in re-enrollment visits.
3. Subjects must be in a stable neurological condition, relapse-free and free of any corticosteroid treatment [intravenous (IV), intramuscular (IM) and/or per os (PO)] or adrenocorticotropic hormone (ACTH), 60 days prior to re-enrollment.
4. Women of child-bearing potential (for example women who are not postmenopausal or surgically sterilized) must practice an acceptable method of birth control for 30 days before taking the study drug and two acceptable methods of birth control during the study and up to 30 days after the last dose of the study treatment was administered. Acceptable methods of birth control in this open label extension phase include: intrauterine devices, barrier methods (condom or diaphragm with spermicide) and hormonal methods of birth control (e.g. oral contraceptive, contraceptive patch, long-acting injectable contraceptive).
5. Subjects must be willing and able to comply with the protocol requirements for the duration of the study.
6. Subjects must be able to comprehend, sign and date a written informed consent prior to re-enrolling into the LAQ/5063 OL study.

Exclusion Criteria for returning subjects

Any of the following conditions will exclude the subject from re-enrolling into the study:

1. Premature discontinuation from the LAQ/5063 OL study, for any reason, except planned pregnancy.
2. Subjects with progressive forms of MS or other non RRMS variant of neuroinflammatory or demyelinating diseases.
3. Use of experimental or investigational drugs and/or participation in drug clinical studies within 6 months prior to re-enrollment visit.
4. Use of immunosuppressive agents, or cytotoxic agents, including cyclophosphamide and azatioprine within 12 months prior to re-enrollment visit.
5. Use of either of the following within 2 years prior to re-enrollment: natalizumab (Tysabri®), rituximab, ocrelizumab, atacicept, belimumab, or ofatumumab.
6. Previous treatment with glatiramer acetate (Copaxone®), IFN-β (either 1a or 1b), fingolimod (Gilenya®), dimethyl fumarate (Tecfidera) or IV immunoglobulin (IVIG) within 2 months prior to re-enrollment visit.
7. Use of teriflunomide (Aubagio®) within- 2 years prior to re-enrollment, except if active washout (with either cholestyramine or activated charcoal) was done 2 months or more prior to randomization.
8. Use of mitoxantrone (Novantrone) within 5 years prior to re-enrollment in subjects with normal ejection fraction and who did not exceed the total lifetime maximal dose.
9. Previous use of cladribine and alemtuzumab (Lemtrada).
10. Previous total body irradiation or total lymphoid irradiation.
11. Previous stem cell treatment, autologous bone marrow transplantation, or allogenic bone marrow transplantation.
12. Acute infection within 2 weeks prior to re-enrollment visit.
13. Major trauma or surgery within 2 weeks prior to re-enrollment visit.
14. Use of moderate/strong inhibitors of CYP3A4 within 2 weeks prior to re-enrollment visit.
15. Use of inducers of CYP3A4 within 2 weeks prior to re-enrollment visit.
16. Pregnancy [according to serum β-hCG test performed within 7 days prior to re-initiation of treatment] or breastfeeding.
17. Serum levels $\geq 3 \times \text{ULN}$ of either ALT or AST at re-enrollment visit.
18. Serum direct bilirubin which is $\geq 2 \times \text{ULN}$ at re-enrollment visit.

19. Subjects with clinically significant or unstable medical or surgical condition detected or worsened during the LAQ/5063 OL study, which preclude safe participation and completion of the LAQ/5063 OL study.
20. Any malignancies, excluding basal cell carcinoma, in the 5 years prior to re-enrollment.
21. Subjects who underwent endovascular treatment for Chronic Cerebrospinal Venous Insufficiency (CCSVI) within 3 months prior to re-enrollment.

Table 12: Study Task Flow Chart for Returning Subjects (Month 24 onwards)

Visit	V10E1	V11E1	V12E1	V13E1	V14E1	V15E1	V16E1	Every 6 months	Termination/Early Discontinuation	Unscheduled Visit ^a
Month	24E1	30E1	36E1	42E1	48E1	54E1	60E1			
Informed consent ^b	X						X			
Inclusion/exclusion criteria	X									
Concomitant medications	X	X	X	X	X	X	X	X	X	X
Cardiovascular risk factor assessment and management ^c	X		X		X		X	Every 12 months from Month 72		
ECG	X	X	X	X	X	X	X	X	X	X
Neurological examination	X	X	X	X	X	X	X	X	X	X
Evaluation of relapse ^d	X	X	X	X	X	X	X	X	X	X
Ascertaining the use of effective contraception	X	X	X	X	X	X	X	X	X	X
Serum and urine β hCG ^e (on site)	X	X	X	X	X	X	X	X	X	X
Urine β hCG (self check, at home); pregnancy tests mandatory phone calls ^f	EVERY 1 MONTH BETWEEN VISITS									
Adverse events	X	X	X	X	X	X	X	X	X	X
Vital signs ^g	X	X	X	X	X	X	X	X	X	X
Physical examination	X	X	X	X	X	X	X	X	X	X
Safety laboratory evaluation (CBC, chemistry, GFR estimation, markers of inflammation)	X	X	X	X	X	X	X ^h	X ^h	X ^h	X ^h
Laquinimod dispensing and accountability	X	X	X	X	X	X	X ⁱ	X	X ⁱ	X
Subject compliance	X	X	X	X	X	X	X	X	X	X

Visit	V10E1	V11E1	V12E1	V13E1	V14E1	V15E1	V16E1	Every 6 months	Termination/Early Discontinuation	Unscheduled Visit ^a
Month	24E1	30E1	36E1	42E1	48E1	54E1	60E1			
Termination documentation and notification of early termination									X	
Unscheduled samples										X ^j

Subjects who are discontinued from study treatment will be encouraged to continue all scheduled visits and procedures until completion of both study periods (with the exception of procedures associated with drug dispensing and accountability, pregnancy testing, and GFR estimation [including body weight measurement]).

^a Assessments during an unscheduled visit will be performed as deemed necessary by the Investigator, except for vital signs and adverse events, which are mandatory at each visit

^b At Month 24 (visit 10) of the open label phase Informed Consent will be signed for the extended open label period of 36 months. At Month 60 (visit 16) of the open label phase an Informed Consent will be signed for the additional extension as long as the Sponsor continues the development of laquinimod 0.6 mg for RRMS

^c In addition, an evaluation should take place as soon as possible for subjects already in the study, following approval of Amendment #10

^d Relapse evaluation will be performed in scheduled as well as unscheduled visits as deemed necessary by the Investigator/Coordinator

^e For women of child-bearing potential

^f Mandatory phone calls will be performed within 72 hours of the scheduled home pregnancy test

^g Weight will be measured at all visits

^h Inflammatory markers will not be collected from Month 60 and onwards

ⁱ Only drug retrieval

^jUnscheduled urgent safety laboratory samples, pharmacokinetic blood samples, and/or samples for potential biomarker analyses may be collected at the discretion of the investigator or medical monitor at any time to assist with further investigations of cardiovascular events or other clinical event of interest. The samples should be collected as soon as possible in association with the event.

Date: _____ Subject No.: _____

HOME PREGNANCY TEST QUESTIONNAIRE

Date of contacting the subject: _____ / _____ /
DD MM YY

Name of site staff person to contact the subject _____

Date in which home urine pregnancy test was performed: _____ / _____ /
DD MM YY NDHome urine pregnancy test result: Positive/negative

IF HOME URINE PREGNANCY TEST WAS NOT PERFORMED:

Was a urine pregnancy test scheduled?
Yes NoIf yes – specify the date for which the next contact was scheduled _____ / _____ /
DD MM YY

